8.2.2 Secondary Endpoints

Secondary endpoints include:

- 8.2.2.1 Assessment of other PK parameters (e.g. C_{max} , t_{max} , $t_{1/2}$, CL) of the phase 0 microdose compared to the therapeutic dose.
- 8.2.2.2 Comparison of the PK parameters of the phase 0 microdose to the FOLFOX-integrated microdose.
- 8.2.2.3 The association of oxaliplatin-DNA adducts (see **section 10.3**) and tumor response by RECIST 1.1 (see **Appendix C**).
- 8.2.2.4 The association of oxaliplatin-DNA adducts (see **section 10.3**) and duration of disease control (see **Appendix C**).
- 8.2.2.5 Safety according to the Common Terminology Criteria for Adverse Events version 4 (see **section 7.2**).

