11.2.2 Secondary Analyses

Given the small number of patients included in this pilot study, all secondary analyses will be considered hypothesis generating for the design of future confirmatory study.

11.2.2.1 For secondary endpoint 8.2.2.1, we will correlate PK parameters from microdosing with parameters from therapeutic doses of oxaliplatin. All parameters will be normalized for dose. We will present descriptive summaries (scatterplots, tables, mean, SD,

correlation coefficient) of the relationship between the two sets of parameters.

11.2.2.2 For secondary endpoint 8.2.2.2, we will correlate PK parameters from phase 0 microdosing with parameters from FOLFOX-integrated microdosing of oxaliplatin. We will present descriptive summaries (scatterplots, tables, mean, SD, correlation coefficient) of the relationship between the two sets of parameters.

11.2.2.3 For secondary endpoint 8.2.2.3 and 8.2.2.4, we will characterize the repair of DNA adducts in PBMC, using descriptive statistics (graphical summaries, mean, SD, box plots). Response rate and duration of disease control (DDC) will be measured according to RECIST 1.1 (**Appendix C**). The DDC is equivalent to progression free survival if an intermittent oxaliplatin strategy is not employed. Progression free survival will be calculated from the date of enrollment to the date of first objective evidence of radiographic progression (soft tissue or bone lesion) or date of death due to any cause, whichever occurs first. If an intermittent oxaliplatin strategy is chosen, we will define DDC as the addition of the initial PFS and the PFS of the reintroduction, except in case of progression at the first evaluation after FOLFOX reintroduction. Radiological assessment by the treating Investigator will be the primary report in this analysis. We hypothesize that higher levels of DNA repair will be associated with non-response and shorter duration of disease control.

11.2.2.4 For secondary endpoint 8.2.2.5, we will assess toxicity to both micordoses of [¹⁴C]oxaliplatin. Toxicities potentially related to [¹⁴C]oxaliplatin will be assessed from initiation of the study to at least 14 days after the administration of the FOLFOX-integrated microdose or until full recover of toxicity (whichever is longer). Safety will be assessed through summaries of adverse events and laboratory evaluations. Descriptive statistics will be used rather than inferential statistics.

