11.3 Sample Size

The number of subjects required to provide 80% probability that a 95% CI for the ratio of geometric means of full dose and micro dose PK parameters is within 2 fold (i.e., from 0.5 to 2) depends on the coefficient of variation (CV) of the ratio of the parameters, which depends on the CV of each parameter and the within-person correlation between the full dose and micro dose parameters (on a log scale). According to the Lappin et al. [77], CVs for $t_{1/2}$ were in the 0.3-0.5 range for diazepam and midazolam (which had good concordance between doses as well as adequate bioavailability). With these specifications, a sample size of 6 patients receiving both full- and micro-doses is sufficient.

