Non-measurable disease. All other lesions (or sites of disease), including small lesions (longest diameter <10 mm or pathological lymph nodes with ≥ 10 to <15 mm short axis), are considered non-measurable disease. Bone lesions, leptomeningeal disease, ascites, pleural/pericardial effusions, lymphangitis cutis/pulmonitis, inflammatory breast

disease, and abdominal masses (not followed by CT or MRI), are considered as non-measurable.

Note: Cystic lesions that meet the criteria for radiographically defined simple cysts should not be considered as malignant lesions (neither measurable nor non-measurable) since they are, by definition, simple cysts.

'Cystic lesions' thought to represent cystic metastases can be considered as measurable lesions, if they meet the definition of measurability described above. However, if non-cystic lesions are present in the same patient, these are preferred for selection as target lesions.

Target lesions. All measurable lesions up to a maximum of 2 lesions per organ and 5 lesions in total, representative of all involved organs, should be identified as **target lesions** and recorded and measured at baseline. Target lesions should be selected on the basis of their size (lesions with the longest diameter), be representative of all involved organs, but in addition should be those that lend themselves to reproducible repeated measurements. It may be the case that, on occasion, the largest lesion does not lend itself to reproducible measurement in which circumstance the next largest lesion which can be measured reproducibly should be selected. A sum of the diameters (longest for non-nodal lesions, short axis for nodal lesions) for all target lesions will be calculated and reported as the baseline sum diameters. If lymph nodes are to be included in the sum, then only the short axis is added into the sum. The baseline sum diameters will be used as reference to further characterize any objective tumor regression in the measurable dimension of the disease.

Non-target lesions. All other lesions (or sites of disease) including any measurable lesions over and above the 5 target lesions should be identified as **non-target lesions** and should also be recorded at baseline. Measurements of these lesions are not required, but the presence, absence, or in rare cases unequivocal progression of each should be noted throughout follow-up.

Methods for Evaluation of Measurable Disease

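### The adduct–response analysis names no measure of association and treats tumour response only as a RECIST response rate in about six patients; adding percent change in target-lesion sum would be a cheap gain

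*Combined protocol and SAP*

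**What the plan says.** Objective 1.2.3 is to measure PBMC adducts and correlate them with response and progression-free survival. Section 8.2.2.3 makes the endpoint the association of adducts "and tumor response by RECIST 1.1"; Section 8.2.2.4 adds a separate association with duration of disease control (DDC).

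Section 11.2.2.3 covers both. It describes adduct repair with graphs, means, SDs and box plots, and then says "Response rate and duration of disease control (DDC) will be measured according to RECIST 1.1". Its hypothesis links more repair to non-response and shorter disease control. It names no statistic for the association. Sections 11.2.2.1 and 11.2.2.2, just above it, do name scatterplots and correlation coefficients for the PK comparisons.

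Under Target lesions, Appendix C says the sum of diameters "for all target lesions will be calculated and reported as the baseline sum diameters". Its response criteria define partial response as a fall of at least 30% from baseline, and progression as a rise of at least 20% (and at least 5 mm) from the smallest sum, or new lesions. Section 7.3 repeats imaging every 8 weeks for 6 months and then every 12 weeks, in patients with measurable disease.

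Section 11.3 concludes that "a sample size of 6 patients receiving both full- and micro-doses is sufficient". Section 11.2.2 labels all secondary analyses hypothesis generating.

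**The concern.** A response rate in six patients is a yes/no outcome. It treats a 31% and a 90% shrinkage alike, and likewise a 29% shrinkage and a 19% growth from baseline. The percent change that separates these patients must be worked out anyway to assign the category, yet it appears in no analysis.

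The stake is modest but specific. Section 11.2.1 says the adduct data will count in deciding the assay's future, and Section 11.2.2 says the secondary results serve the design of a confirmatory study. Such a design needs some idea of how strong the association is. A comparison of perhaps two responders with four non-responders gives almost none, and if all patients fall in one group there is no comparison.

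**Working it through.** **1. The plan's own figure.** Section 11.3 sizes the trial for "80% probability that a 95% CI for the ratio of geometric means" to lie between 0.5 and 2. Take a true ratio of 1, log-SD = √ln(1+CV²), and a t-based interval inside ±ln 2. With CV 0.3 / 0.4 / 0.5 read as the CV of the ratio, the smallest N by simulation is 5 / 6 / 8, and the probability at N=6 is 0.99 / 0.87 / 0.66. If the CV is that of each parameter, a within-person correlation of 0.5 gives the same N; the plan states no correlation. Six is therefore reproducible, but only for the PK ratio. No size, alpha or power is stated for adducts against response.

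**2. Smallest attainable exact two-sided p, n=6.** For a split of k against 6−k it is 2/C(6,k):
- 3 v 3: 2/20 = 0.10
- 2 v 4: 2/15 = 0.133
- 1 v 5: 2/6 = 0.333

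For a rank correlation without ties it is 2/6! = 2/720 = 0.0028, which needs a perfect ordering. These values gauge information only; the plan specifies no test.

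**3. Information kept by a yes/no split** (bivariate normal, responder fraction p): φ(z_p)²/[p(1−p)].
- p=0.3: 0.348²/0.21 = 0.58
- p=0.4: 0.386²/0.24 = 0.62
- p=0.5: 0.399²/0.25 = 0.64

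At p=0.2 it is 0.49. The fractions are assumptions. Section 2.5 cites 46% for BSA-dosed FOLFOX patients in one study, which gives 0.63.

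**4. Information kept by ordered categories.** Assume 20% PD, 40% SD and 40% PR. The mean normal scores of the groups are −1.400, −0.266 and 0.966. The share kept is 0.2×1.960 + 0.4×0.071 + 0.4×0.933 = 0.79.

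**5. Chance of exact p ≤ 0.10, n=6** (same category shares, so 40% responders; 20,000 simulations):

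| True correlation | Percent change | Ordered category | Yes/no |
|---|---|---|---|
| 0.8 | 44% | 40% | 13% |
| 0.6 | 23% | 23% | 8% |

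Repeat runs moved these by one or two points. Most of the loss comes from dichotomising, and keeping the order recovers most of it.

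**6. No contrast at all.** The chance that all six fall in one response group is p⁶+(1−p)⁶: 26% at p=0.2, 12% at 0.3, 3% at 0.46. With four measurable patients it is 41%, 25% and 13%.

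**7. Precision after the change.** For an observed correlation of 0.7 at n=6, Fisher's z is 0.867 ± 1.96/√3 = 0.867 ± 1.132, giving about −0.26 to 0.96.

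**The case against.** A reader might infer that the plan commits to a responder/non-responder comparison. It does not. The means, SDs and box plots in Section 11.2.2.3 describe adduct repair, no two-group test is named, and Section 8.2.2.3 refers to RECIST response, which has ordered levels. The response rate and the wording of the hypothesis suggest a split without fixing one. This stands: the figures against a yes/no split are conditional on that reading, and the gain over ordered categories at n=6 is small.

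A reader might also infer that percent change could replace RECIST response at no cost. Appendix C does not support that. New lesions or unequivocal non-target progression count as progression whatever the target lesions do, so such a patient could look like a good responder. Patients with only non-measurable disease have no sum, although Appendix C can still classify them. Measurable disease is not an inclusion criterion in Section 4.1, so fewer than six may contribute; with four patients the smallest Spearman p is 0.083, and with three it is 0.33. This also stands.

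DDC is already planned as a time outcome that counts new lesions and death, so response is not the only clinical outcome examined. But DDC is a separate endpoint, and it does not supply an association measure for tumour shrinkage.

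Finally, a correlation cannot be run as things stand, because the adduct variable is undefined: PBMCs are sampled repeatedly, endpoint 8.2.2.3 speaks of adducts, and the hypothesis concerns repair. That gap has to be closed in the same edit.

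**Conclusion.** The point holds as a cheap improvement to a descriptive secondary analysis. Section 11.2.2.3 leaves the association measure and the adduct summary open, and carries response as a rate although a finer outcome is already recorded. If response is read as yes/no, p cannot go below 0.10 with six patients and about 58–64% of the information is kept, assuming 30–50% responders and bivariate normality. The chance of p ≤ 0.10 at a true correlation of 0.8 falls from about 44% to about 13%; ordered RECIST categories bring it back to about 40% under the assumed category shares.

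The documents do not support calling the analysis invalid: it is labelled hypothesis generating, has no alpha or power, and does not touch the primary PK endpoint. Nor will the change make the association precise.

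**What to change.** In Section 11.2.2.3, keep the RECIST response rate and DDC, and add beside them:

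- One pre-named PBMC adduct summary: the level at a stated time point, or a repair rate, chosen to match the stated hypothesis.
- A scatterplot and Spearman correlation, with confidence interval, of that summary against best percent change from baseline in the sum of target diameters, in patients with measurable disease. Show RECIST category as the plotting symbol and report the number contributing.
- A rule for new-lesion and non-target progression: rank as worst those patients whose best overall response is progression for that reason, or flag them and repeat the correlation that way.
- A companion rank correlation with ordered RECIST category (CR/PR/SD/PD).
- A sentence that these results are descriptive and hypothesis generating.

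The cost is wording and a small amount of programming; no new scans, samples or patients are needed. The downsides are a possibly smaller number of patients, an outcome that by itself misses part of progression, and a wide interval.

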1.2 Secondary Objectives

- 1.2.1 To estimate the degree to which a [¹⁴C]oxaliplatin microdose predicts the observed pharmacokinetics of standard dose oxaliplatin
- 1.2.2 To validate that intrapatient variation of exposure to a [¹⁴C]oxaliplatin microdose is less than 5%
- 1.2.3 To detect the levels of oxaliplatin-DNA adducts induced by oxaliplatin microdosing in peripheral blood mononuclear cells (PBMC), and correlate the results with patient response and progression free survival on oxaliplatin-based chemotherapy
- 1.2.4 To develop preliminary safety data of [¹⁴C]oxaliplatin microdosing for future studies

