6.6 Follow Up Period

Patients will remain on study until progression of disease or until any of the criteria in **section 6.7** are met. If an intermittent oxaliplatin strategy is chosen, the time of progression will be defined as progression after the first reintroduction of oxaliplatin, as has previously been defined [79, 80].

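### Objective 1.2.3 relates adducts to PFS, but the analysis uses only DDC, which can add a second period for intermittent-oxaliplatin patients; Sections 6.6 and 11.2.2.3 also date their progression differently.

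*Combined protocol and SAP*

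**What the plan says.** Objective 1.2.3 is to measure oxaliplatin-DNA adducts in PBMCs and "correlate the results with patient response and progression free survival on oxaliplatin-based chemotherapy". The matching endpoint, 8.2.2.4, is the association of adducts "and duration of disease control". The hypothesis that closes Section 11.2.2.3 is also worded in terms of DDC.

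Section 11.2.2.3 treats DDC and PFS as the same thing when oxaliplatin is not given intermittently. For an intermittent strategy, "we will define DDC as the addition of the initial PFS and the PFS of the reintroduction". The sum carries one qualifier: "except in case of progression at the first evaluation after FOLFOX reintroduction". Appendix C repeats the sum and the exception.

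The progression event is described in two places:

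- Section 11.2.2.3: "Progression free survival will be calculated from the date of enrollment to the date of first objective evidence of radiographic progression", or to death if that comes first. No exception is made for intermittent patients.
- Section 6.6, for an intermittent strategy: "the time of progression will be defined as progression after the first reintroduction of oxaliplatin".

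Sections 6.5.2 and 7.4 leave dosing after cycle 1 to the treating investigator. Section 11.2.2 calls all secondary analyses hypothesis generating.

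**The concern.** There are two linked problems.

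First, the outcome named in the objective is never related to adducts. PFS is defined in Section 11.2.2.3, but for intermittent patients it serves only as a component of DDC. One outcome variable thus holds a single period for some patients and the sum of two for others. Which patients can gain a second period depends on a treatment decision made after cycle 1, outside the protocol's control. With 6 evaluable patients planned (Section 11.3), one or two intermittent patients could shape the picture, and nothing provides for marking them or analysing them separately.

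Second, two sections give different dates for the same event in the same patient. A data manager following Section 6.6 would record a later progression date than an analyst following Section 11.2.2.3. Read literally, Section 6.6 gives no progression date to an intermittent patient who progresses and is never reintroduced.

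The protocol's own reasoning makes a link between strategy and biomarker conceivable. Section 8.2.1.1 ties total exposure to neuropathy, Section 2.2 says neurotoxicity leads to interruption of treatment, and Section 2.2 also ties adduct formation to drug concentration. This is a possible path and has not been shown.

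**Working it through.** The plan states no figure for PFS, DDC or their relation to adducts, so there is nothing to reproduce. The check is algebraic, followed by one illustration.

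**Algebra.** Let PFS1 be the time to first progression or death (Section 11.2.2.3) and PFS2 the PFS of the reintroduction, with PFS2 > 0.

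- Continuous patient: DDC = PFS1.
- Intermittent patient, second period added: DDC = PFS1 + PFS2.
- Intermittent patient, progression at the first evaluation after reintroduction: DDC = PFS1, reading the exception as adding nothing.

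So DDC − PFS1 is either 0 or PFS2. DDC is never below PFS1, and it exceeds PFS1 exactly when the second period is added. The relative excess is PFS2 / PFS1.

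The Section 6.6 date is calendar time: PFS1 + gap before reintroduction + PFS2. It is later than the Section 11.2.2.3 date even when the exception applies to DDC.

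**Illustration.** Assumed: first progression at week 40, reintroduction at week 42, imaging counted from reintroduction. From Section 7.3: imaging every 8 weeks for 6 months, then every 12 weeks. The documents do not say which interval applies after reintroduction, so both are shown.

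| Patient | PFS (11.2.2.3), weeks | DDC, weeks | Time of progression (6.6), weeks |
|---|---|---|---|
| Continuous | 40 | 40 | 40 (the special rule does not apply) |
| Intermittent, progression at first evaluation after reintroduction | 40 | 40 | 42 + 8 = 50, or 42 + 12 = 54 |
| Intermittent, progression at second evaluation | 40 | 40 + 16 = 56, or 40 + 24 = 64 | 42 + 16 = 58, or 42 + 24 = 66 |

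All three patients have the same first progression. In the last row DDC exceeds PFS by 16 / 40 = 40% or 24 / 40 = 60%. The two progression dates for one patient differ by 50 − 40 = 10 to 54 − 40 = 14 weeks in the second row, and by 58 − 40 = 18 to 66 − 40 = 26 weeks in the third.

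With PFS to first progression or death as the common event, all three patients score 40 weeks.

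**The case against.** The best defence is that DDC is a deliberate choice, stated in advance. It is consistent across 8.2.2.4, 11.2.2.3 and Appendix C, and its relation to PFS is explained. The objective speaks of PFS on oxaliplatin-based chemotherapy. Under an intermittent strategy, first progression may come while oxaliplatin is paused, so it need not indicate resistance to the drug. PFS to first progression in everyone would mix progression on and off oxaliplatin, and so would also depend on strategy. This stands. It is a reason to keep DDC, but it does not explain why the outcome named in the objective goes unreported.

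A second defence is that Section 6.6 is a follow-up section and its sentence only says how long intermittent patients stay on study. That is probably the intent, but the words define a time of progression, and they conflict with Section 11.2.2.3 as written.

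Two stronger readings are tempting and should be resisted.

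- A reader might infer that DDC is longer for every intermittent patient. The exception for progression at the first evaluation after reintroduction rules this out.
- A reader might infer that the reintroduction period is counted twice, by taking the Section 6.6 date as the end of the initial PFS. Section 11.2.2.3 ends PFS at first radiographic progression and names the initial PFS and the PFS of the reintroduction as separate parts. Its formula does not count any period twice.

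**Conclusion.** The point holds and is minor. The objective and the endpoint name different outcomes. Sections 6.6 and 11.2.2.3 can give an intermittent patient two progression dates. For such a patient DDC is equal to or longer than PFS, so an association with adducts can partly reflect the strategy chosen. This does not make DDC a wrong endpoint, and the documents do not establish that strategy depends on adduct level.

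The 40% to 60% excess rests on assumed times, on reintroduction after first progression, and on progression at the second evaluation; other timings give other figures, including zero. The documents do not say whether any of the planned patients will use an intermittent strategy. The analysis is descriptive, with no formal test or model of adducts against DDC specified, and the primary PK endpoint is untouched.

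**What to change.** 1. Reword Section 6.6 so that it states only how long intermittent patients are followed, and does not define the time of progression.
2. State in Section 11.2.2.3 that the PFS event is first progression or death for all patients, whatever the strategy.
3. Under 8.2.2.4 and 11.2.2.3, report the association of adducts with PFS for every patient, as objective 1.2.3 says. Show the pre-specified DDC beside it, with intermittent patients identified in tables and plots.
4. In the same edit, settle one start date for PFS: Section 11.2.2.3 counts from enrollment, Appendix C from the start of treatment.

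The cost is a few sentences. No new data are needed, because the date of first progression is already required to calculate the initial PFS within DDC.

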6.3.2 Modification of the radioactive microdose during the study

We will vary the radioactive dose of [¹⁴C]oxaliplatin (dpm/kg) in the patient's microdose by combining the [¹⁴C]oxaliplatin with unlabeled oxaliplatin until the desired radioactive dose and chemical microdose (total dose at 1/100th of the therapeutic dose) are obtained. This effectively varies the radiochemical specific activity of the microdose infusion. The dose of [¹⁴C]oxaliplatin (dpm/kg) for this feasibility study will be determined by measuring the ¹⁴C associated with genomic DNA isolated from patient's PBMCs after microdosing. A ¹⁴C signal 10-100 times background is acceptable for this study. Of note, the sensitivity for pharmacokinetic analysis is much higher and we do not expect dose modification to have any impact on pharmacokinetic feasibility.

We will start [¹⁴C]oxaliplatin at 2 X 10⁶ dpm/kg of body weight, and add unlabeled oxaliplatin to 1% of the therapeutic oxaliplatin as calculated based on the dose of 85 mg/m². This dose level was demonstrated to be adequate and safe in a single breast cancer patient in a prior study. Two patients will be recruited to this dose level (Dose

Level 1). If the ^{14}C signal in PBMC genomic DNA is sufficient, dose level 1 will be used for the rest of the study. If the ^{14}C signal is insufficient or too high, the dose level will be titrated up or down, respectively, based on the ^{14}C signal as outlined in **Table 1**, and administered to two additional patients per dose level until a sufficient ^{14}C signal is obtained. If no ^{14}C signal can be detected in the genomic DNA at Level 3, no further escalation will be performed.

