7.3 Efficacy Assessments

For the purposes of this study, screening tumor assessments using CT of the chest/abdomen/pelvis and other areas of known disease or newly suspected disease should be performed within 28 days prior to registration. Scans of the abdomen, pelvis and other areas of the body may be done with MRI instead of CT, but evaluation of the chest should be done with CT. CT scans should be performed with iodinated IV contrast and MRI scans with IV gadolinium chelate unless there is a medical contraindication to contrast. If iodinated IV contrast is contraindicated, chest CT should be done without IV contrast. The CT component of a combined PET/CT may be used as long as the slice thickness is < 5 mm.

For the purposes of this study, patients with radiographically measurable disease at baseline should be re-evaluated for response every 8 weeks (+/- 1 week) for 6 months and then every 12 weeks (+/- 2 weeks) thereafter. The interval in imaging may be changed after discussion with the principal investigator. Response and progression will be evaluated in this study using the international criteria proposed by the revised Response Evaluation Criteria in Solid Tumors (RECIST) guideline (version 1.1) [Eur J Ca 45:228-247, 2009]. Changes in the largest diameter (unidimensional measurement) of the tumor lesions and the shortest diameter in the case of malignant lymph nodes are used in the RECIST criteria. Please see **Appendix C** for RECIST 1.1 criteria.

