10 SPECIAL INSTRUCTIONS

10.1 Specimen Collection, Storage, Shipping and Submission Requirements

10.1.1 Collection Method and Storage

One 8-ml blood specimen will be collected into a BD Vacutainer CPTTM tube with sodium heparin (Becton Dickinson products # 362753) through an indwelling temporary venous catheter at the time points described in **Table 2** and **Table 3**. The tube will be gently inverted several times to ensure mixing with heparin anticoagulant. The tube will be immediately put on ice. To isolate plasma, the tubes are centrifuged at room temperature in a horizon rotor for 25 minutes at 1600 X g. After centrifugation, plasma is located at the top of the specimen (**Figure 3**), and will be transferred to two polypropylene cryogenic vials. The vials will be labeled with patient's identification information and stored at or below -70°C until shipping. After collection of all of the specimens from the same patients, the ¹⁴C content in plasma is determined by liquid scintillation count. The oxaliplatin concentration is calculated based on the ¹⁴C content in the plasma specimens.

Figure 3. Centrifugation to separate Plasma and Mononuclear Cells in Peripheral Blood

After most of the plasma is removed for PK study, PBMC will be transferred to another tube, washed twice with ice-cold phosphate-buffered solution (PBS) with 2% fetal calf serum. DNA will be extracted from PBMC as described before [67], and sent to Accelerated Medical Diagnostics and LLNL for Pt-DNA adduct measurement.

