16 DATA AND SAFETY MONITORING

This protocol is also subject to the UC Davis Cancer Center's (UCDCC) Data and Safety Monitoring Plan. The UCDCC is committed to pursuing high-quality patient-oriented clinical research and has established mechanisms to ensure both scientific rigor and patient safety in the conduct of clinical research studies. The UCDCC relies on a multi-tiered committee system that reviews and monitors all cancer clinical trials and ensures the safety of its participants, in compliance with institutional and federal requirements on adverse event (AE) reporting, verification of data accuracy, and adherence to protocol eligibility requirements, treatment guidelines, and related matters. The Scientific Review Committee (SRC) assumes overall oversight of cancer studies, with assistance and input from two independent, but interacting, committees: the Quality Assurance Committee and the Data Safety Monitoring Committee. A multi-level review system strengthens the ability of the UCDCC to fulfill its mission in conducting high quality clinical cancer research.

As per University of California Davis Cancer Center (UCDCC) Clinical Trials Support Unit (CTSU) SOP AM 506: Protocol Specific Meetings, the principal investigator (PI), clinical research coordinator (CRC), and the clinical research nurse meet at least monthly for ongoing study information, to discuss patient data and adverse events and to determine if dose escalation is warranted, when applicable.

According to the UCDCC Data and Safety Monitoring Plan (DSMP), any new serious adverse events related to the drugs being used on this trial are reviewed monthly by the UCDCC Data and Safety Monitoring Committee (DSMC) and any applicable changes to the study are recommended to the PI, if necessary.

The UCDCC Scientific Review Committee (SRC) determines if a UCDCC Data and Safety Monitoring Board (DSMB) is required. If required, the DSMC will appoint a DSMB. The DSMB is responsible for reviewing study accrual logs, adverse event information and dose escalation meeting minutes (where applicable) to ensure subject safety and compliance with protocol defined guidelines.

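### Readers of response and progression are not masked to adduct results, and dose titration makes at least the first two patients' adduct signals known to the study team

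*Combined protocol and SAP*

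**What the plan says.** **Who scores outcome.** Section 11.2.2.3, on response and duration of disease control: "Radiological assessment by the treating Investigator will be the primary report in this analysis". The same section gives a direction: "We hypothesize that higher levels of DNA repair will be associated with non-response and shorter duration of disease control". Appendix C provides one limited second look: exceptional progression in non-target lesions alone is to be confirmed later by a review panel or the principal investigator.

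**Who sees the adduct signal.** Under 6.3.2 the radioactive dose "will be determined by measuring the ¹⁴C associated with genomic DNA isolated from patient's PBMCs after microdosing". Two patients start at Level 1. If their signal is sufficient, that level is kept for the rest of the study. If not, the next level is "administered to two additional patients per dose level until a sufficient" signal is found. Section 16 has the principal investigator, research coordinator and research nurse meet at least monthly "to discuss patient data and adverse events and to determine if dose escalation is warranted", qualified as applying when applicable. Section 10.3 says adduct levels will be reported but names no recipient, date or restriction.

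**Who can influence outcome timing.** Section 7.3: "The interval in imaging may be changed after discussion with the principal investigator". Section 7.4 leaves dose changes and delays after the start of Cycle 1 to the treating investigator.

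**Status of the analysis.** Section 11.2.2 calls all secondary analyses hypothesis generating. Section 11.2.1 adds that the totality of the data, including adduct formation in PBMCs, will guide future development of the assay.

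**The concern.** Endpoints 8.2.2.3 and 8.2.2.4 ask whether adducts go with response and duration of disease control. An unmasked reader who knows the predictor and holds a directional hypothesis can, without intent, call a borderline scan the expected way. Discretion over scan intervals could also move a progression date. Section 11.3 plans six patients, so one or two such calls can shape the whole picture. Calling the analysis hypothesis generating excuses low precision. It does not excuse a directional error that a line of text would prevent, least of all when adduct data will inform whether and how the assay is developed.

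**Working it through.** The plan gives no figure on this point, so there is none to reproduce. The check has three parts.

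**1. Is there a path from biomarker to outcome scoring?**
- Predictor: the titration signal is ¹⁴C in PBMC genomic DNA (6.3.2). Section 2 hypothesises that accumulated microdose-induced damage in this DNA correlates with response.
- Timing: the signal arises after the phase 0 microdose. FOLFOX starts 2 days to 4 weeks later (6.1), and scans follow every 8 weeks (7.3). Assay turnaround is not stated, but titration has to be settled before patients at the next level are dosed, so the signal can be known before outcomes are scored.
- Roles: the principal investigator attends the escalation meeting (16), is consulted on scan intervals (7.3) and may confirm non-target progression (Appendix C).
- Barrier: none is stated.

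**2. How many signals must be reviewed?** Two patients per level visited (6.3.2, Table 1):

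| Levels used | Signals reviewed | Share of 6 |
|---|---|---|
| 1 only | 2 | 2/6 |
| 1 then -1, or 1 then 2 | 4 | 4/6 |
| 1, 2 and 3 | 6 | 6/6 |

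The shares assume that titration patients count among the six evaluable patients, which the documents do not say.

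**3. How far could the association move?** All inputs except the six patients are assumptions: no true association; 2 clear responders, 2 clear non-responders and 2 patients near the RECIST 30% cut; all 720 adduct orderings equally likely. A borderline patient with an unknown signal is called at random. One with a known signal is always called in line with rank (upper three = response). Concordance is the share of responder/non-responder pairs in which the responder has the higher adduct level.

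Full enumeration, by number *j* of borderline patients whose signal is known:

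| *j* | Concordance | Perfect separation |
|---|---|---|
| 0 | 0.500 | 5.8% |
| 1 | 0.5875 | 10.0% |
| 2 | 0.675 | 16.7% |

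Check of the first row: there are 2, 3 or 4 responders with probability 1/4, 1/2, 1/4, so perfect separation is 1/4 × 1/15 + 1/2 × 1/20 + 1/4 × 1/15 = 0.058.

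If *k* of the six signals are known, *j* has probability C(2,*j*) × C(4,*k*−*j*) / C(6,*k*).
- *k* = 2 (weights 6/15, 8/15, 1/15): concordance 0.2000 + 0.3133 + 0.0450 = 0.558; perfect separation 0.0233 + 0.0533 + 0.0111 = 0.088.
- *k* = 4 (weights 1/15, 8/15, 6/15): concordance 0.0333 + 0.3133 + 0.2700 = 0.617; perfect separation 0.0039 + 0.0533 + 0.0667 = 0.124.
- *k* = 6: 0.675 and 0.167.

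With a single borderline patient, concordance is 0.5875 if all signals are known and 0.50 + 0.0875 × 2/6 = 0.53 if two are known.

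**A softer version.** Take 3 high-adduct and 3 low-adduct patients, true response 50% in both, known signals split evenly between the groups, and each known patient's reading pushed toward the hypothesis with probability *f*. The high group gains *f* × 0.5 × (*k*/2)/3 = *fk*/12 and the low group loses the same, so the spurious difference in response rate is *fk*/6. For *f* from 10% to 30% that is 3 to 10 points (*k* = 2), 7 to 20 (*k* = 4) or 10 to 30 (*k* = 6).

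**The case against.** The best reply is that this is a pilot. The adduct endpoints are secondary, summarised descriptively without a test, and the primary endpoint is a PK ratio that no scan reading can touch. RECIST 1.1 thresholds and a default scan schedule limit discretion. The stated hypothesis in 11.2.2.3 concerns repair, while titration uses signal over background, and the development clause in 11.2.1 names adduct formation rather than its link with response. All of this stands as a limit on importance. None of it supplies masking, and Section 2 ties adduct accumulation itself to response.

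Several stronger readings are tempting and are not supported:
- *Every patient's adduct value reaches the scan reader.* Titration requires review only until a level is accepted, as few as two patients. For the rest the gap is missing masking, not required disclosure.
- *The people who see the signal are the sole readers of the scans.* Section 16 names the principal investigator, coordinator and nurse in general institutional wording; 11.2.2.3 names the treating investigator. Overlap is plausible at one centre but not stated, and Appendix C allows a limited second look.
- *Specimen labels unmask the biomarker.* The sentence "The vials will be labeled with patient's identification information" in 10.1.1 concerns plasma vials for PK, not the DNA used for adducts, and the identification may be the unique patient number assigned under Section 12.
- *0.68 and 17% are what to expect.* They require all six signals and their ranks to be known and every borderline call to follow them.

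**Conclusion.** The concern holds in a limited form: outcome readers are not masked to adduct results, and titration makes at least two patients' signals (four or six if levels change) known to a team whose principal investigator also has a hand in scan timing and some progression calls. The exposed result is the descriptive adduct-outcome association only.

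With two borderline patients in six, the worst-case shift in concordance is from 0.50 to about 0.56 with two signals known and to 0.68 with six; the chance of perfect separation goes from about 6% to 9% and 17%. These are upper bounds under full alignment, not forecasts. They rest on the assumed number of borderline patients, on the reader knowing the ranks, and on titration patients being among the six. The case for acting is that the bias is directional and almost free to prevent, not that it is shown to be large.

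**What to change.** - **6.3.2 and 16:** the laboratory reports to the study team only whether the signal is below, within or above 10-100 times background. The titration rule needs nothing more. A coarse leak remains if two patients fall in different bands.
- **10.3 and 11.2.2.3:** individual adduct values are not released to anyone who assesses response or progression or decides scan timing until that patient's best response and progression status are entered, or a named data cutoff is reached. The cutoff matters because follow-up runs to progression, and some patients may not progress.
- **Leave microdose PK results unrestricted.** Microdose AUC is part of the primary endpoint, and holding it back until progression would delay the main result for the sake of a secondary one.

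Cost: protocol wording and a reporting instruction to the laboratory, with no added reader, visit or sample. The downside is that investigators do not see individual adduct values in real time.
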